## SYNOPSIS

Study Title	Postpartum depression after Cesarean delivery: Ketamine as a preventative intervention. A feasibility pilot-study (PoCKet Pilot).												
Primary Objective	To assess the feasibility of the study by establishing: a) the incidence of PPD in our cohort; b) the acceptability to eligible patients; c) the ability of the investigative team to collect the data and; d) the tolerability of the interventions.												
Hypothesis	We hypothesize that ketamine reduces the incidence of postpartum depression (PPD) when administered at cesarean delivery and that the subcutaneous route is well tolerated and has a favorable pharmacokinetic profile.												
Study Period	Planned enrolment duration: 52 weeks Planned study duration: 58 weeks												
Number of Participants	60 patients (20 in each of the subcutaneous [SC], intravenous [IVI] and control [P] groups)												
Study Intervention	Patients in each group will receive both subcutaneous (s/c) and intravenous (i.v.) administration of their corresponding injectate shortly after delivery of their baby. The injectate will consist of either 0.9% Sodium Chloride (N/S) or 50 mg/ml ketamine (Ket) depending on their group allocation. The s/c injectate will be administered undiluted whereas the i.v. injectate will be diluted to make up a 40 ml infusion. 
  
 Groups	s/c injectate	i.v. injectate	
   
 SC:	Ket	N/S	
 
 IVI:	N/S	Ket	
 
 P:	N/S	N/S	
  
	Groups	s/c injectate	i.v. injectate	SC:	Ket	N/S	IVI:	N/S	Ket	P:	N/S	N/S
Groups	s/c injectate	i.v. injectate											
SC:	Ket	N/S											
IVI:	N/S	Ket											
P:	N/S	N/S											
Study Design	A randomised, double-blind, placebo-controlled feasibility pilot study												
Eligibility Criteria	
Inclusion criteria
 
 
1. Term pregnancy
 
2. Age 18-45 years of age
 
3. Scheduled cesarean delivery under neuraxial anesthesia
 
 
Exclusion criteria
 
 
1. ASA classification IV or V
 
2. History of psychotic episodes
 
3. History of allergy to ketamine
 
4. Inability to communicate in English or any other barrier to providing informed consent
 
												
Measurements	
 
Psychosocial stress (Antenatal Risk Questionnaire [ANRQ])
 
Weight (kg) and height (m)
 
Time of delivery of baby
 
Total intraoperative dose of analgesic/sedative medication
 
Baseline and intraoperative vital signs
 
Maximum intraoperative pain (NRS)
 
48-hour total opiate consumption (morphine equivalents)
 
Apgar scores at 1 and 5 minutes postpartum
 
Admission to NICU
 
												

	
 
j) Pain originating from surgical site (NRS 0-10): 2, 6, 24 and 48 hours and 21 and 42 days postpartum.
 
k) Edinburgh Postpartum Depression Scale (EPDS) and Generalized Anxiety Disorder 7-item (GAD-7) Scale: Day of surgery and postpartum days 1, 2, 21 and 42
 
l) Plasma concentrations of ketamine at baseline, 20, 40 and 100 minutes after administration
 
m) Breastfeeding success (Y/N): postpartum days 1 and 2
 
n) Adverse effects, intraoperatively and at 2 and 6 hours postpartum (absent, mild, moderate or severe)
 

Statistical Methodology	
Descriptive statistics will be employed to present the demographic data. Continuous variables will be summarized using means (SD) or medians (IQR), as appropriate. After construction of the concentration-time curves for each patient, the peak plasma concentration and area under the concentration-time curve will be summarized overall and associations with both antidepressant effect and incidence of adverse symptoms will be explored.
 
NONMEM® 7.4 (ICON Development Solutions) software will be utilised to assess pharmacokinetic profile of ketamine by each route.

## 1. BACKGROUND AND SIGNIFICANCE

### 1.1 Postpartum depression (PPD)

PPD is one of the most common perinatal medical complications and can have a detrimental effect on both mother and baby. Suicide exceeds hemorrhage and hypertensive disorders as a cause of maternal mortality and maternal psychopathology interferes with the parent-infant relationship. It has been estimated to have a period prevalence of 19.2% in the first 3 postpartum months. The rapid decline in reproductive hormones is thought to contribute to the development of PPD in susceptible women, although the specific pathogenesis is unknown. The American College of Obstetricians and Gynecologists recommend that all women should be routinely screened for depressive symptoms in the perinatal period. The strongest risk factor is history of pre-existing mood disorder and Robertson et al. list additional risk factors (Table 1) for PPD in the postpartum period.

---

• Depression during pregnancy

• Traumatic birth experience

• History of depression

• Anxiety during pregnancy

	

• Breastfeeding problems

• Preterm birth/infant admission to neonatal intensive care (NICU)

---	---

---

**Table 1:** Risk factors for PPD

### 1.2 Ketamine's anti-depressant effect

Ketamine, a phencyclidine derivative, is a non-competitive antagonist at the N-methyl-D-aspartic acid (NMDA) receptor that is commonly used as an anesthetic or sedative agent and has proven analgesic effect after a variety of surgeries including CD, where it has also been shown to reduce shivering. It has been demonstrated to have a rapid anti-depressant effect in treatment-resistant depression outside of pregnancy. The most commonly employed intravenous (IV) dose for this purpose is 0.5 mg/kg over 40 minutes, as single or repeated infusions. It has been postulated that prolonged blockade of NMDA receptors causes long-term changes in signal transduction leading to sustained clinical improvement, some investigators have explored longer term infusions such as those used to treat chronic pain. A recent pilot study assessing the feasibility of a 96-hour (~0.5mg/kg/hr) infusion compared with a single 40-minute (0.5 mg/kg) infusion suggested a trend toward greater efficacy in the prolonged infusion but confirmation of a statistically significant result is awaited.

### 1.3 Ketamine and PPD

This promising anti-depressant effect has prompted investigation of ketamine as a preventative measure in patients undergoing CD. There have been 2 studies to date, one which failed to demonstrate any benefit from a bolus dose of 0.25 mg/kg and one which documented a large reduction (1 and 22% in the treatment and control, respectively) in the (6 week) period prevalence of postpartum depression after a 4 mg/kg dose of ketamine over 50 hours (~0.08 mg/kg/hr).

The prolonged IV infusion, in the Jianxin (2015) study, was achieved by adding the ketamine to a sufentanil patient-controlled analgesic (PCA) pump with a background infusion. This PCA pump is a standard part of their post-cesarean analgesic regimen. In our institution, it is standard practice to discontinue IV infusions and to remove IV cannulae as early as it is safe to do so. This practice is essential to the attempts to enhance postoperative recovery and aid mother's bonding with their babies and facilitate their early-

life care. This reflects patients' expectations and preferences and is in line with other maternity units across North America and Europe.

The natural course of PPD varies and, although it may resolve spontaneously within weeks, approximately 20% of women with PPD still have depression at 12 months and beyond. As many as 13% will still have depressive symptoms at 2 years and 40% will have a relapse. Considering the maternal suffering, disruption to the family, potential impairment of the social, emotional, and cognitive development of the child, and the rare cases of infanticide and suicide caused by PPD, the impact on families and society as a whole is difficult to overemphasize. An intervention that promises such a large reduction in this devastating disease warrants extensive research. In an attempt to achieve the benefit demonstrated by Jianxin et al. whilst employing methods more acceptable to our patients we have designed a pilot study to assess the feasibility of our study design and collect preliminary tolerability and efficacy data on ketamine administered by two alternative routes: 40-minute IV infusion (i.v.) and subcutaneous (s.c.) injection.

## 2 OBJECTIVES

- 2.1 To determine the feasibility of performing this study at our institution
- 2.2 To determine the pharmacokinetic profiles of ketamine when administered as a subcutaneous injection and an intravenous infusion at cesarean delivery
- 2.3 To obtain preliminary data to inform the design of a randomized controlled trial to assess the efficacy of ketamine as a preventive intervention at cesarean delivery against PPD

## 3 PATIENT SELECTION

- 3.1 Inclusion criteria:
  - 3.1.1 Term pregnancy
  - 3.1.2 Age 18-45 years of age
  - 3.1.3 Scheduled cesarean delivery under neuraxial anesthesia
- 3.2 Exclusion criteria:
  - 3.2.1 ASA classification IV or V
  - 3.2.2 History of psychotic episodes
  - 3.2.3 History of allergy to ketamine
  - 3.2.4 Inability to communicate in English or any other barrier to providing informed consent
- 3.3 Inclusion of women and minorities:
  - 3.3.1 Eligible pregnant women of all ethnicities and cultures presenting to the Barnes Jewish Hospital Labor & Delivery floor will be invited to participate in this research

## 4 REGISTRATION PROCEDURES

- 4.1 Confirmation of patient eligibility
  - 4.1.1 We will screen all patients scheduled for cesarean delivery and confirm their eligibility by assessing their: i) age; ii) gestational age; iii) medical history and; iv) allergy history.
- 4.2 Assignment of unique participant number
  - 4.2.1 Each patient will be identified with a unique participant number (UPN) for this study. All data will be recorded with this identification number on the appropriate case report form (CRF).
- 4.3 Randomization
  - 4.3.1 Patients will be randomly assigned to one of the three groups: SC, IVI or Control. The randomization will be performed in 1:1:1 ratio in blocks of 6, with no stratifications.

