## 5 STUDY DESIGN

- 5.1 This will be a double-blinded, placebo-controlled, feasibility pilot study. The primary outcomes are related to the ability of the study procedures to gather data on the interventions' efficacy in preventing postpartum depression. Successful attainment of the following feasibility milestones (FM) is necessary to justify proceeding with a pragmatic clinical trial:
  - 5.1.1 **FM1:** Establish that the incidence of PPD in our cohort is >10%
  - 5.1.2 **FM2:** Achieve the recruitment of >50% of approached patients to demonstrate feasibility for an RCT
  - 5.1.3 **FM3:** Ensure that the design of assessments and data collection make it possible to achieve a complete dataset in >90% of participants

5.1.4 **FM4:** Ascertain that none of chosen routes of administration of ketamine is intolerable to patients, as defined as the incidence of one or more severe side effects experienced by >10% of participants in that study arm.

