## 6 STUDY PROCEDURES

6.1 Participants will be assigned to one of three intervention groups (Table 2).

Groups	Subcutaneous injectate	Intravenous injectate*
SC (n=20)	50 mg/ml ketamine	0.9% Sodium Chloride
IVI (n=20)	0.9% Sodium Chloride	50 mg/ml ketamine
P (n=20)	0.9% Sodium Chloride	0.9% Sodium Chloride

**Table 2:** Intervention groups. \*the i.v. injectate will be diluted up to a 40 ml infusion.

6.2 Participants will have baseline data (Table 3) recorded on the relevant case report form on the day of delivery. This data will include demographics to assess the performance of randomization procedures as well as characteristics that have been demonstrated to confer an increased risk of PPD. The patient will be prepared for cesarean as per institutional protocols.

Measure	Units/values
Age	Years
Height	Metres
Weight (day of surgery)	Kilograms
Gestational age	Weeks
Ethnicity	White, Black/African American, Asian, Native American/Alaskan natives, Native Hawaiian, Pacific Islander, Hispanic/Latino
Insurance status	Insured/uninsured
Psychiatric history	PPD, major depressive disorder (MDD), anxiety, premenstrual syndrome (PMS), premenstrual dysphoric disorder (PMDD), mood disorder, personality disorder, psychotic disorder
Current anxiety and depressive symptoms	EPDS and GAD-7
Psychosocial stress	ANRQ

**Table 3:** Baseline data

Once an adequate sensory block is achieved, surgery will commence. Upon delivery of the baby, 0.01 ml/kg of the “*subcutaneous injectate*” will be injected subcutaneously and the “*intravenous injectate*” will be made up to a 40ml infusion (Table 4) and commenced at 60 ml/hr. Both injectates will be administered/initiated approximately 0 - 5 minutes after delivery by the anesthetic provider via one of the cannulae that they will be using for standard patient care. The intravenous study infusion will be prepared by a member of the investigative team, who will not be involved in data collection.

---

Add 0.01 ml/kg of the “*IVI study solution*” to a 60ml syringe and use 0.9% sodium chloride to dilute the solution to 40ml.

---

**Table 4:** Instructions for preparing the “*IVI study infusion*”

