### Measurements:

1. Baseline data
2. EPDS and GAD-7 scores at baseline and approximately 1, 2, 21 and 42 days postpartum

3. ANRQ at baseline
4. Time of delivery of baby
5. Total intraoperative dose of any analgesic/sedative medication
6. Incidence of hypo- or hypertension (systolic BP < 80 or > 170 mmHg, respectively) and brady- or tachycardia (pulse < 40 or > 120 bpm, respectively)
7. Maximum intraoperative pain (numerical rating scale [NRS], 0-10)
8. Incidence of the signs/symptoms in Table 5 will be assessed intraoperatively and approximately 2 and 6 hours after delivery. The presence of each adverse effect will be assessed using a 4-point scale (absent, mild, moderate, severe).

Nausea	Shivering	Blurred vision
Vomiting	Anxiety	Diplopia
Pruritus	Euphoria	Nystagmus
Dizziness	Hallucinations	
Sedation	Amnesia	

**Table 5:** Adverse effects

9. Surgical site pain (NRS) at 2, 6, 24 and 48 hours, as well as 21 and 42 days, postpartum.
10. Opiate consumption in the first 48 hours (measured in morphine equivalents) will be calculated.
11. Plasma concentrations of ketamine at baseline and approximately 20, 40 and 100 minutes postpartum.

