## 9 STATISTICAL METHODS

### 9.1 Sample size and analysis

No formal sample size has been performed as this is a pilot designed to establish the feasibility of an RCT. Preliminary data from this study will be used to inform the sample size calculation for the subsequent clinical trial. Descriptive statistics will be employed to present the demographic data. Continuous variables will be summarized using means (SD) or medians (IQR), as appropriate. After construction of the concentration-time curves for each patient, the peak plasma concentration and area under the concentration-time curve will be summarized overall and associations with both antidepressant effect and incidence of adverse symptoms will be explored.

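### Section 4.3.1 prints one fixed block size of 6 and the plan describes no allocation concealment, so up to 29% of ketamine-or-saline statuses could be deduced in advance; varying, undisclosed blocks would cut this to about 4%

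*Combined protocol and SAP*

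**What the plan says.** Section 4.3.1 sets out the allocation: "Patients will be randomly assigned to one of the three groups: SC, IVI or Control", followed by "The randomization will be performed in 1:1:1 ratio in blocks of 6, with no stratifications". The Synopsis plans "60 patients (20 in each of the subcutaneous [SC], intravenous [IVI] and control [P] groups", which is ten complete blocks.

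Section 5 describes the blinding: "This will be a double-blinded, placebo-controlled, feasibility pilot study". Every woman receives an injectate by both routes, with saline in place of ketamine where the arm requires it (Table 2). Section 6.2 keeps the person who prepares the intravenous infusion out of data collection, but does not mention recruitment. Under Measurements, item 8, "Incidence of the signs/symptoms in Table 5 will be assessed intraoperatively and approximately 2 and 6 hours after delivery"; Table 5 includes euphoria, hallucinations, nystagmus, diplopia and sedation.

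The plan does not say how the sequence is generated, who holds it, how each assignment is released, or whether recruiting and treating staff are kept from knowing the block size.

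**The concern.** With a fixed block whose size is printed in the protocol, the last places of each block follow from the earlier ones for anyone who can work out what earlier women received. Saline by both routes hides the route. It does not hide a drug effect such as those in Table 5. Someone who saw those effects and also had a say in enrolment could, even without intending to, bring forward or defer a woman at higher risk of postpartum depression (PPD) according to the treatment expected next.

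The quantities exposed are those reported by arm: the placebo-arm PPD rate, any difference between arms in depression scores, and so the preliminary data that objective 2.3 and section 9.1 intend for designing and sizing the later trial.

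**Working it through.** **Inputs.** From section 4.3.1 and the Synopsis: three arms, 1:1:1, block size 6, N = 60. Hence 60/3 = 20 per arm, 60/6 = 10 blocks, and each block holds 4 ketamine and 2 saline places. The plan gives no predictability figure to reproduce and no recognition rate; the recognition rates below are assumptions.

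**Ceiling: ketamine told from saline without error.** With *j* places left in a block (counting the next one), the next status is certain if all *j* are of the same kind. The probability is p(j) = [C(4,j) + C(2,j)] / C(6,j) for j ≥ 2, and p(1) = 1.

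- p(1) = 1
- p(2) = (6 + 1)/15 = 0.467
- p(3) = 4/20 = 0.200
- p(4) = 1/15 = 0.067
- p(5) = p(6) = 0

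The sum is 1.733 per block. Divided by 6 this is 13/45 = 28.9%; over ten blocks it is 17.3 of 60 women.

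**Exact arm, same observer.** A forced ketamine status does not separate SC from IVI, so the arm is known only when the remaining places are all placebo: C(2,1)/C(6,1) + C(2,2)/C(6,2) = 0.333 + 0.067 = 0.4 per block. That is 0.4/6 = 6.7%, or 4 of 60. The other 1.33 of the 1.73 forced places say only that some form of ketamine comes next.

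**All three arms recognised without error.** [1 + 3·C(2,2)/C(6,2)]/6 = 1.2/6 = 20%, or 12 of 60.

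**Imperfect recognition.** If each earlier call is right with probability *q*, a place with *j* left is forced, with all 6 − j earlier calls right, with probability p(j)·q^(6−j). Summing over j = 1 to 4 and dividing by 6:

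| q | Sum per block | Share |
|---|---|---|
| 1.0 | 1.733 | 28.9% |
| 0.9 | 0.590 + 0.306 + 0.146 + 0.054 = 1.096 | 18% |
| 0.8 | 0.328 + 0.191 + 0.102 + 0.043 = 0.664 | 11% |
| 0.7 | 0.168 + 0.112 + 0.069 + 0.033 = 0.381 | 6% |

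**Delay.** If the status of the most recent woman is still unseen at the next enrolment, certainty needs j + 1 like places: [p(2) + p(3) + p(4)]/6 = 0.733/6 = 12%. If two are unseen: [p(3) + p(4)]/6 = 0.267/6 = 4%. The Synopsis plans 60 women in 52 weeks, or 364/60 ≈ 6 days apart on average, so the 6-hour assessment would usually precede the next enrolment.

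**Varying block sizes.** A simulation of 1,500 trials used an observer with perfect recognition who knows the set of sizes but not their order. The certain share is about 10% for sizes 3 and 6, 5% for 6 and 9, and 4% for 3, 6 and 9. A single fixed size of 3 would be worse (44%); a fixed 9 still gives 21%.

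**The case against.** The strongest reply is that 29% describes an observer who may not exist. It needs known block boundaries, known enrolment order and error-free recognition of every earlier woman in the block. Table 5 is an assessment checklist without expected rates, and the plan does not show that entries such as nausea, pruritus or shivering are specific to ketamine. Section 4.1.1 screens all patients scheduled for cesarean delivery and section 3.3.1 says eligible women will be invited, which limits discretion. This stands: 29% is an upper bound and not an expected rate.

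A reader might infer that staff who see drug effects also recruit, and so that selective enrolment is likely. The documents do not say this. They do not separate the roles either, so the exposure is possible but not shown. Nor does silence on concealment prove that none is in place.

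The design also limits the damage. Section 9.1 states "No formal sample size has been performed as this is a pilot designed to establish the feasibility of an RCT", the analysis is descriptive, and no between-arm test is planned. FM1 to FM3 are defined on the whole cohort or on those approached. FM4 is judged within each ketamine arm.

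A reader might also infer that allocation must be stratified, because section 1.1 says "The strongest risk factor is history of pre-existing mood disorder". The documents do not support this as a requirement in a descriptive pilot of 60. Section 6.2 records "as well as characteristics that have been demonstrated to confer an increased risk of PPD", so imbalance will be visible. The plan gives no prevalence for the factor. At an assumed 30%, with women's histories independent, some two of the three arms differ by 5 or more of 20 women with probability 0.26 (0.17 at 20%, about 0.31 at 40%). That is the worst of three pairs: for one given pair it is 0.12, and for pooled ketamine against placebo a gap of 25 points or more has probability about 0.06. Two strata combined with blocks of 3, 6 and 9 would leave unequal arm totals in about 67% of trials, with differences up to 6.

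**Conclusion.** The point holds as a cheap improvement to the allocation method. A printed, fixed block of 6 with no described concealment allows certain foreknowledge of at most 28.9% of ketamine-or-saline statuses. It would be wrong to say that staff can know 29% of assignments: even the perfect observer of ketamine against saline knows the exact arm for only 6.7%. Under assumed recognition of 70% to 90% the status figure is about 6% to 18%.

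The consequence is a risk of selective enrolment affecting mainly the arm-level data for objective 2.3. Nothing here undermines FM1 to FM3. The size rests on assumed recognition rates and on the unstated overlap between staff who observe and staff who enrol. Lack of stratification is not a defect that must be corrected.

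**What to change.** In section 4.3.1, replace the fixed block size with wording such as: *Allocation is 1:1:1 in randomly permuted blocks of varying size. The sizes are not stated in this protocol. The list is generated and held by a person with no part in recruitment or assessment.* Add a sentence on how each assignment is released once a woman is enrolled.

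Sizes of 3, 6 and 9 would serve, recorded only in a restricted document, with their sequence chosen to total 60 so that 20 per arm is kept. Certain foreknowledge then falls from 28.9% to about 4%. That figure is for freely drawn sizes; an observer who also knew that the sizes total 60 could deduce somewhat more near the end of the list.

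The cost is a new list and a few sentences. If recruitment stops inside a block, arm totals could differ by up to 3 (a block of 9 holds three of each arm), against up to 2 with blocks of 6. Stratification by mood-disorder history may be considered, but is not part of this change.

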## 5 STUDY DESIGN

- 5.1 This will be a double-blinded, placebo-controlled, feasibility pilot study. The primary outcomes are related to the ability of the study procedures to gather data on the interventions' efficacy in preventing postpartum depression. Successful attainment of the following feasibility milestones (FM) is necessary to justify proceeding with a pragmatic clinical trial:
  - 5.1.1 **FM1:** Establish that the incidence of PPD in our cohort is >10%
  - 5.1.2 **FM2:** Achieve the recruitment of >50% of approached patients to demonstrate feasibility for an RCT
  - 5.1.3 **FM3:** Ensure that the design of assessments and data collection make it possible to achieve a complete dataset in >90% of participants

5.1.4 **FM4:** Ascertain that none of chosen routes of administration of ketamine is intolerable to patients, as defined as the incidence of one or more severe side effects experienced by >10% of participants in that study arm.

